Interventions will be evaluated through a pre- and post-intervention survey regarding parental/adolescent's healthy lifestyle knowledge and behaviors developed from nationally approved health surveys including the National Survey of Children's Health (NSCH), the WHO (Five) Well-Being Index, the Patient Health Questionnaire- 9 (PHQ-9), and the Youth Risk Behavior Surveillance System (YRBSS) (Bureau, n.d.; Kroenke et al., 2001; *CDC*, 2021; *WHO-5 Questionnaires*, n.d.). The World Health Organization (Five) Well-Being Index questions will appear in the REDCap survey as a screening prior to the project survey. This survey is suitable for children nine years and above. If the raw score is below 13 or if the patient has answered 0 to 1 to any of the five items, they will not be allowed to complete the REDCap survey or participate in the project (*The World Health Organisation- Five Well-Being Index (WHO-5)*, n.d.; World Health Organization. Regional Office for Europe, 1998).

The pre- and post-intervention survey will be the same, except the post-intervention survey will not include demographic questions. The adolescent survey will include 61 questions total: 6 WHO-5 mental health screening, 7 demographics, 2 weight/self-image, 16 nutrition, 10 PA, 12 sleep, 5 screen time, 4 home environment, and 1 comment box for questions regarding nutrition, PA, screen time, and sleep. The parent/legal guardian(s) survey will include 70 questions total: 4 adolescent mental health screening, 11 demographics, 7 evaluating adolescent overall health, 16 nutrition, 10 PA, 12 sleep, 5 screen time, 4 home environment, 1 comment box for questions regarding nutrition, PA, screen time, and sleep. 1 question will be added to the end of the post-intervention survey (for both adolescent and parent/legal guardian surveys) to assess the impact of the Zoom moderator on the educational intervention. See Appendix.

- 1.5 Provide a description of all research procedures being performed and when they are performed, including procedures being performed to monitor subjects for safety or minimize risks.
 - This project utilizes a one-group pretest-posttest design study for 30 adolescents (aged 12-17 years) diagnosed with a mental health condition(s) and their parent/legal guardian.
 - This will be an educational program delivered via a 45-minute presentation delivered via Zoom.
 - Participants can select between multiple dates/times (over a 3-week period) for educational session.

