- 1.6 The pre- and post-intervention survey will be the same, except the post-intervention survey will not include demographic questions. The adolescent survey will include 61 questions total:6 WHO-5 mental health screening, 7 demographics, 2 weight/self-image, 16 nutrition, 10 PA, 12 sleep, 5 screen time, 4 home environment, and 1 comment box for questions regarding nutrition, PA, screen time, and sleep. The parent/legal guardian(s) survey will include 70 questions total: 4 adolescent mental health screening, 11 demographics, 7 evaluating adolescent overall health, 16 nutrition, 10 PA, 12 sleep, 5 screen time, 4 home environment, and 1 comment box for questions regarding nutrition, PA, screen time, and sleep. 1 question will be added to the end of the post-intervention survey (for both adolescent and parent/legal guardian surveys) to assess the impact of the Zoom moderator on the educational intervention.

1.7 Describe:

- Procedures performed to lessen the probability or magnitude of risks.
 - Parental Consent and Adolescent Assent
 - o Parental Involvement in educational intervention
 - Adolescent mental health screening- The World Health Organization (Five) Well-Being Index questions
 - a. If the raw score is below 13 or if the adolescent has answered 0 to 1 to any of the five items, they will not be allowed to complete the REDCap survey or participate in

the project, unless they are currently enrolled in outpatient mental health services (Ex: counseling, therapy, partial hospitalization).

- All drugs and devices used in the research and the purpose of their use, and their regulatory approval status. N/A
- The source records that will be used to collect data about subjects. (Attach all surveys, scripts, and data collection forms.)
 - See Appendix A and B
- 1.8 What data will be collected during the study and how that data will be obtained.
 - The data collected will compare the effects of an educational program on healthy lifestyle knowledge and behaviors pre-and post-program (after one month) via a REDCap survey for the adolescent and their parent/legal guardian.
 - The data will be obtained through a REDCap survey.

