 - Adolescent eligibility determined with WHO-5 screening prior to pre-intervention survey.
 - o Parent(s)/legal guardian(s), 18 years old or order, live with adolescents diagnosed with mental health condition(s)
 - o Be able to read/write in English.
 - Exclusion Criteria:
 - o Children <12 years old or >18 years old
 - o Children 12-17 that are wards of the state or any other agency, institution, or entity
 - Adolescent scoring <13 and not currently enrolled in mental health services, or if the adolescent has answered 0 to 1 to any of the five items, on the WHO-5, and not currently enrolled in mental health services.
 - Female participants that report they are pregnant before or after the start of the study will be excluded from the study.

- o Parent(s)/legal guardian(s) < 18 years old
- o Non-legal guardians
- 1.13 Indicate specifically whether you will include or exclude each of the following special populations: (You may not include members of the above populations as subjects in your research unless you indicate this in your inclusion criteria.)
 - Adults unable to consent N/A
- 2.0 Individuals who are not yet adults (infants, children, teenagers): Adolescents, 12-17 years old, with a clinical diagnosis of a mental health condition(s).
 - Pregnant women N/A
 - Prisoners N/A

Vulnerable Populations*

- 2.2 If the research involves individuals who are vulnerable to coercion or undue influence, describe additional safeguards included to protect their rights and welfare.
 - If the research involves persons who have not attained the legal age for consent to treatments or procedures involved in the research ("children"), review the "CHECKLIST: Children (HRP-416)" to ensure that you have provided sufficient information.: See attached checklist.

Local Number of Subjects N/A

Recruitment Methods

- 2.3 Describe when, where, and how potential subjects will be recruited. If recruitment will involve a non-FSU site, describe whether site approval for recruitment is required, and attach documentation of site approval.
 - When: Project recruitment will be begin in early October 2022.
 - Where:
 - The setting will be the Intensive Outpatient Behavioral Health Program (IOP) and the Partial Hospitalization Program (PHP) and Bridge Program at Wolfson Children's Hospital in Jacksonville, Florida.
 - Study flyers will also be posted on social media platforms (ex: Facebook and Instagram).
 - Baptist Health IRB approval will be obtained.

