13.6 N/A

Withdrawal of Subjects*

- 2.8 Describe anticipated circumstances under which subjects will be withdrawn from the research without their consent.
 - o Children <12 years old or >18 years old
 - Children 12-17 that are wards of the state or any other agency, institution, or entity
 - Adolescent scoring <13 and not currently enrolled in mental health services, or if the adolescent has answered 0 to 1 to any of the five items, on the WHO-5, and not currently enrolled in mental health services
 - o Parent(s)/legal guardian(s) < 18 years old
 - o Non-legal guardians
- 2.9 N/A
- 2.10 Describe procedures that will be followed when subjects withdraw from the research, including partial withdrawal from procedures with continued data collection.
 - Subject may withdraw from the study at any time. If subjects withdraw from the research, any of their data will be destroyed and their collected data will not be included in the final data analysis.

Risks to Subjects*

2.11 Participants in this project will be at Minimal risk-means that the probability and magnitude of harm or discomfort anticipated in the research are not greater in and

of themselves than those ordinarily encountered in daily life or during the performance of routine physical or psychological examinations or tests.

- Participants may feel embarrassed with some of the questions that I will ask
- Taking the survey and joining the educational presentation may make participants tired.
- 2.12 N/A
- 2.13 N/A
- 2.14 N/A

Potential Benefits to Subjects*

- 2.15 Improved nutrition, physical activity, screen time, and sleep education influenced by healthy lifestyle knowledge and behaviors. This project intends to improve healthy lifestyle knowledge and behaviors among adolescents with a mental health condition(s) through preventative and detailed nutritional, physical activity, screen time, and sleep education.
- 2.16 N/A

Data Management* and Confidentiality

- 2.17 Data will then be analyzed using SPSS version 27.0. Descriptive statistics for adolescent and their parent/legal guardian's demographic characteristics will be computed. The analysis of this project will compare changes in healthy lifestyle knowledge and behaviors and knowledge using a paired t-test.

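### The WHO-5 withdrawal rule has no time point and the WHO-5 block is repeated in the post-survey, so a literal build could block one-month outcomes for adolescents outside services who score low

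*Combined protocol and SAP*

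**What the plan says.** - **Withdrawal (section 2.8).** The prompt reads "Describe anticipated circumstances under which subjects will be withdrawn from the research without their consent". One of the circumstances listed under it is "Adolescent scoring <13 and not currently enrolled in mental health services", together with any of the five items answered 0 to 1 by someone not in services. No time point is attached.
- **Exclusion (section 1.12).** The same rule appears as an entry exclusion: "Adolescent scoring <13 and not currently enrolled in mental health services, or if the adolescent has answered 0 to 1 to any of the five" WHO-5 questions. The inclusion list gives a time: "Adolescent eligibility determined with WHO-5 screening prior to pre-intervention survey".
- **Survey content (sections 1.4 and 1.6).** "The pre- and post-intervention survey will be the same, except the post-intervention survey will not include demographic questions". The only stated addition is one question about the Zoom moderator. The adolescent survey is itemised as "6 WHO-5 mental health screening, 7 demographics, 2 weight/self-image, 16 nutrition, 10 PA, 12 sleep, 5 screen time", and so on. The WHO-5 block is therefore counted apart from the demographics that are dropped.
- **Position and function (section 1.4).** "The World Health Organization (Five) Well-Being Index questions will appear in the REDCap survey as a screening prior to the project survey". An adolescent who fails it may not go on with the REDCap survey or take part.
- **Exemption.** Sections 1.7, 1.11, 1.12 and 2.8 spare adolescents currently in mental health services. Section 1.4 and the flyer criteria in section 2.5 state the rule without that exemption.
- **Data after withdrawal (section 2.10).** Data of subjects who withdraw are destroyed and left out of the final analysis. The text does not say whether this covers withdrawal by the study team.
- **Analysis (section 2.17).** A paired t-test of pre/post change. The goal is 30 dyads, there is no control group, and no method for missing data is given.

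**The concern.** A score rule that acts only at entry defines who is studied. The same rule acting at one month decides whose outcome is observed, using a measurement taken after the intervention. Well-being plausibly moves with sleep, activity and screen time, so the missing pairs would not be a random subset.

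The 45-minute session is over by then, so withdrawal at that point prevents no exposure to it and costs only the outcome. If section 2.10 also applies, the baseline record goes too, and the loss could not be examined later. With about 30 dyads and no control group, each avoidable loss matters, and outcomes never collected cannot be recovered at analysis.

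**Working it through.** The plan states no figure on this point to reproduce, so the main check is of the text.

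**1. Is the WHO-5 asked again at one month?** Yes, on the text. Only demographics are removed, and the 6 WHO-5 questions are listed separately from the 7 demographic questions.

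**2. Does it come before the outcome items?** Yes. Section 1.4 places "questions will appear in the REDCap survey as a screening prior to the project survey".

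**3. Is the cutoff applied at one month?** Not stated. Section 1.12 dates the eligibility decision before the pre-survey. Section 2.8 is a withdrawal list with no date. No section says that the post-survey WHO-5 is scored against the cutoff, and none says that it is not.

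**4. Whom would it reach under 2.8?** Adolescents not in services who score below 13, or answer any item 0 to 1, at one month. A fall in well-being that stays clear of both limits triggers nothing. Recruitment is from intensive outpatient, partial hospitalization and Bridge programs and also through social media, so the share outside services is unknown.

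**5. How large could the selection be?** All inputs below are assumptions; none is in the documents. Let u be the share not in services, q the fraction of those removed (taken as the lowest WHO-5 changes), and ρ the correlation of WHO-5 change with outcome change. In SD of outcome change:

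retained mean minus enrolled mean = u·ρ·φ(z_q) / (1 − u·q)

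pairs kept = 30·(1 − u·q)

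For q = 0.3, φ(z_q) = 0.348. With ρ = 0.5:

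| u | Gap (SD) | Pairs kept |
|---|---|---|
| 0 | 0 | 30 |
| 0.25 | 0.25 × 0.5 × 0.348 / 0.925 = 0.05 | 27.75 |
| 0.5 | 0.5 × 0.5 × 0.348 / 0.85 = 0.10 | 25.5 |
| 1 | 1 × 0.5 × 0.348 / 0.70 = 0.25 | 21 |

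With ρ = 0 the gap is zero and only precision is lost. For a two-sided 5% paired t-test (alpha and sidedness assumed), the change detectable with 80% power is 0.53 SD with 30 pairs, 0.56 with 27 and 0.64 with 21. This table ranks removals by change, whereas the rule acts on the one-month score, so it is a stylised range.

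**6. The rule itself, simulated.** Assumptions: five items scored 0 to 5, total mean 14 to 18, SD 4 to 5, retest correlation 0.6 to 0.8, nobody in services, no true change, and behaviour change correlated 0.2 to 0.4 with WHO-5 change. Of those passing at entry, about 5% to 27% fail at one month. The retained mean behaviour change exceeds the enrolled mean by about 0.01 to 0.13 SD.

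**7. What that gap is.** With no true change, the condition of passing at both times treats the two occasions alike, so the mean WHO-5 change among those retained is zero, and so is any behaviour change that follows it linearly. The simulation agrees: the retained mean is about 0 and the enrolled mean about −0.01 to −0.13 SD. The enrolled mean is negative because of regression to the mean after an entry cutoff. The gap is therefore between retained and enrolled adolescents.

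**The case against.** The strongest reply is that section 2.8 simply describes screen failures. Assent is the first section of the REDCap survey, so an adolescent who fails the WHO-5 has already agreed, and removal is then formally without consent. The protocol uses withdrawal in this sense elsewhere, for mismatched ages and for refusing the screening questions. The 2.8 list largely copies the 1.12 exclusions, and some entries, such as a child under 12, cannot arise after valid entry. Where a rule is meant to run past entry the protocol says so, as it does for pregnancy in 1.12. The survey appendices are not in the available text, so no gate on the post-survey can be confirmed.

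Most of this stands. It makes an entry-only intention plausible and means that removal at one month is an inference. It does not close the gap: 1.12 dates eligibility but does not limit 2.8, and a survey built from 1.4 and 1.6 as written could carry the gate forward.

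A reader might infer more in two ways. One is that adolescents whose well-being falls are removed as a matter of fact. The documents do not say so, and the 2.8 rule reaches only those outside services who cross a cutoff. The other is that the simulated 0.01 to 0.13 SD is upward bias from a true zero. Step 7 shows that it is not. Real deterioration could be hidden by such selection, but that simulation does not demonstrate it.

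**Conclusion.** The point holds as an ambiguity with a real consequence if read one way. The protocol does not say when the 2.8 WHO-5 rule applies, and its own survey description puts the screen ahead of the one-month outcomes. If the rule is applied there, loss of pairs depends on post-intervention well-being, and the retained mean change would tend to look more favourable than that of all enrolled adolescents.

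The size is unknown and probably modest. The simulated gap of up to 0.13 SD assumes nobody in services and is below one standard error with 30 pairs (1/√30 = 0.18 SD). The 0.25 SD corner of the table also needs 30% removed and a correlation of 0.5. The effect shrinks with the share in services and is zero if all are in services and the exemption applies. If the survey follows the version in 1.4 without the exemption, being in services protects no one; those passages must be reconciled.

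This is a low-cost correction worth making, not a demonstrated design failure.

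**What to change.** - In section 2.8, limit the WHO-5 circumstance to the screen before the pre-survey, in line with section 1.12.
- In sections 1.4 and 1.6, state that the post-survey WHO-5 is recorded and that the adolescent continues to the outcome items whatever the score. Confirm that the REDCap post-survey has no gate.
- State that these pairs stay in the paired analysis, and say in section 2.10 whether data destruction covers withdrawals made by the study team.
- Reconcile the passages that give the rule with and without the services exemption.

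How the team responds to a low post-survey score is for the sponsor to set, separately from whether outcome data are kept. The cost is a few sentences and a check of the survey's branching logic. With no removals after entry, this source of selection disappears.

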 - The data will be destroyed approximately five years after the study ends.
- Who will have access to the data or specimens?
 - o [name], [name], [name]
- Who is responsible for receipt or transmission of the data or specimens?
 - o Data will be automatically uploaded into REDCap.
- How data or specimens will be transported?
 - All project data is stored and hosted there at the local institution, and no project data is ever transmitted at any time by REDCap from that institution to another institution or organization.
- The requested disclosure of PHI is the minimum necessary for research purposes. PHI will not be reused or disclosed to any other person or entity, or for other research for which the use or disclosure of protected health information for which an authorization or opportunity to agree or object is not required by 45 CFR 164.512.

Provisions to Monitor the Data to Ensure the Safety of Subjects*

18.1 Study data will be sent to the Research Electronic Data Capture (REDCap) program, a secure, web-based application stored on a secure server at the Florida State University College of Medicine. Only de-identified information will be maintained on the PI's password-protected computer. The data will be accessed only by the PI using a password known only to her. The data will be destroyed approximately five years after the study ends.

2.21 Describe:

- This study is considered a clinical trial because it involves human participant that are assigned an intervention (there is no control). This study is designed to evaluate the effect of the intervention on behavioral outcomes.
- The PI will periodically evaluate the data collected regarding both harms and benefits to determine whether subjects remain safe.
- This study will not engage in any activities that may lead to potential injury for participants.
 - o The data will be reviewed through REDCap questionnaire.
 - The project intervention includes a 45-minute educational presentation via Zoom will include: 5-10 minutes of education regarding recommendations versus reality for nutrition, PA, screen time, and sleep, 20-25 minutes of education regarding ways to improve healthy lifestyle knowledge and behaviors.
- Data from this study will be collected through REDCap survey.
- Data collection will only occur during September November 2022. There will be a pre- and post-intervention survey.
- The PI and Major Professor will review the data.

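### As worded, the post-survey repeats the WHO-5, but the plan gives no safety response if an adolescent outside services first meets its own cutoff at one month

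*Combined protocol and SAP*

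**What the plan says.** **Survey content (1.4, 1.6).** The adolescent survey is listed as containing "6 WHO-5 mental health screening" questions, counted separately from demographics. The parent survey contains "4 adolescent mental health screening" items. On the second administration: "The pre- and post-intervention survey will be the same, except the post-intervention survey will not include demographic questions". Section 1.10 sends the post-survey one month after the session.

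**Entry rule (1.4, 1.7, 1.11, 1.12).** Section 1.4 says that the WHO-5 "questions will appear in the REDCap survey as a screening prior to the project survey", and that a low scorer may neither complete the survey nor take part. Section 1.7 adds an exception for adolescents already in outpatient mental health care. It places "Adolescent mental health screening- The World Health Organization (Five) Well-Being Index questions" under the heading "Procedures performed to lessen the probability or magnitude of risks". Section 1.12 gives the timing: "Adolescent eligibility determined with WHO-5 screening prior to pre-intervention survey".

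**Withdrawal (2.8, 2.10).** Section 2.8 lists the same cutoff, outside services, as a ground for withdrawal without consent. It gives no time point. Section 2.10 says that data from subjects who withdraw are destroyed and left out of the analysis.

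**Monitoring and support (2.21, 2.27).** Section 2.21 says "The PI will periodically evaluate the data collected regarding both harms and benefits to determine whether subjects remain safe". It adds review by the PI and Major Professor, no statistical testing of safety data, and no trigger for suspension. Section 2.27 names liaisons at the hospital programs as a psychological resource, without linking them to a score.

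**The concern.** The participants are minors with a mental health diagnosis. At entry, the plan treats a low WHO-5 score in an adolescent outside services as enough to stop participation, and it classes that screen as a risk-lessening procedure. If the same questions are answered a month later, the study will hold a result that it has itself defined as concerning. The visible text does not say what happens next.

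Adolescents outside services can be in the study. They enrol by passing the screen, and flyers on social media reach families beyond the hospital programs. Those families may have no site liaison.

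The only written consequences of a low score are the survey gate and the withdrawal rule. Neither is a safety response. Applied literally at one month, the first would stop the adolescent from completing the post-survey and the second would remove the adolescent from the study.

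**Working it through.** **Is the WHO-5 repeated?** The survey wording is loose, so its arithmetic comes first.

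- Adolescent items listed in 1.4: 6 + 7 + 2 + 16 + 10 + 12 + 5 + 4 + 1 = 63. The stated total is 61, so it does not reproduce.
- Parent items listed: 4 + 11 + 7 + 16 + 10 + 12 + 5 + 4 + 1 = 70, as stated.

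The 6 WHO-5 items and the 7 demographic items are separate entries, and only the latter are dropped. On the words, the WHO-5 stays. Against this, 1.4 and 1.12 describe it as a screen before the survey, and the adolescent total is off by 2. The repeat is the plain reading, but it is an inference.

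**What follows from a low score at one month?**

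| Text | If it applies at entry only | If it also applies at one month |
|---|---|---|
| Gate in 1.4 and 1.7 | No consequence | Post-survey blocked (under 1.4, even for those in services) |
| 2.8 | No consequence | Adolescent withdrawn |
| 2.21 | No score-linked step | No score-linked step |
| 2.27 | General resource, hospital programs | The same, with no trigger |

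In neither column is the adolescent or family directed to help because of the score. The parent screening items, and the PHQ-9 named in 1.4 as a survey source, also have no follow-up step in the visible text.

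**How many adolescents could this concern?** The documents give no WHO-5 distribution, no share in services and no retention rate. All inputs below except the 30 are assumptions.

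- *Crossing rate p.* Simulation of five items scored 0 to 5: item mean 3.0 or 3.5, latent SD 1.2, inter-item correlation 0.5 or 0.65, one-month stability of the common factor 0.7 or 0.9, and no true change. Entry requires a total of at least 13 and every item at least 2; 64% to 82% pass. Among those who pass, 8% to 23% meet the cutoff a month later. The spread also covers whether item-specific noise partly persists or is fresh at each time.
- *Number at issue n.* Of 30, 70% to 100% complete the post-survey and 10% to 75% of those are outside services: 30 × 0.70 × 0.10 = 2.1, taken as 2; 30 × 1.00 × 0.75 = 22.5, taken as 22.
- *Expected crossings n × p.* 2 × 0.08 = 0.16; 22 × 0.23 = 5.1.
- *Chance of at least one, 1 − (1 − p)^n.* 1 − 0.92² = 0.15; 1 − 0.77²² = 0.997.

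This gives roughly 0 to 5 of 30. The simulation has no true change, so every crossing it counts is ordinary fluctuation around a selected starting point. If almost all recruits come from the hospital programs and are in services, n could be close to zero.

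**The case against.** **The WHO-5 may be a one-time gate.** Sections 1.4 and 1.12 place it before the survey, and the survey forms in Appendices A and B are not shown. If the authors meant a single screen, the gap disappears once the text says so. This stands, and the fix allows for it.

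**Section 2.8 largely repeats the entry exclusions.** Its other entries are age, ward status and guardianship. Where the authors want an exclusion to run on, as with pregnancy in 1.12, they say so. This also stands. A reader might infer that adolescents who worsen will be withdrawn and their data destroyed, biasing the paired comparison. The documents do not support that. It needs 2.8 to apply at one month, and 2.10, which is worded for subjects who themselves withdraw, to cover withdrawal by the study.

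**A help notice may exist out of sight.** Consent, assent and survey forms are the usual place for one, and they are not visible. This limits the point to the visible protocol text.

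**An entry gate is not a notification rule.** The plan attaches no parent notice to a low score even at entry, and the post-survey is the last study activity. A reader might infer that the PI must tell parents about a low score. The documents do not support that either: 2.23 promises adolescents that others will not learn their answers, and 2.20 bars disclosure of PHI. Reversing those promises could reduce candour at the entry screen, which is a safeguard in its own right.

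What survives is narrow: the time point of the rule is unstated in 2.8, and no supportive step is tied to the cutoff.

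**Conclusion.** The point holds as a cheap safety improvement. As worded, the post-survey repeats the WHO-5, and the visible plan has no safety response for an adolescent outside services who first meets the cutoff at one month. The blocking and withdrawal rules are probably for entry only, but one sentence should say so.

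The size cannot be estimated from the documents. Roughly 0 to 5 of 30 is an illustration that rests on an assumed score distribution, services share and retention.

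A reader might take such crossings as a sign that the session does harm. With one group and no control, a crossing cannot be attributed to the session, and the assumed model produces them with no change at all. There is no material effect on the planned t-test, which concerns lifestyle knowledge and behaviors rather than the WHO-5. Use of the WHO-5 at entry is not in question.

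**What to change.** 1. **Fix the time point.** State in 1.4, 1.7 and 2.8 that the WHO-5 rule applies once, before the pre-survey, and that a low post-survey score does not block the survey, withdraw the adolescent or remove data. If a single screen was intended, drop the WHO-5 from the post-survey in 1.4 and 1.6 instead; step 2 is then unnecessary.
2. **If it is repeated, add a resource message.** Have REDCap automatically show the adolescent a message at the same cutoff (raw total under 13, or any item 0 or 1). It should advise talking to the parent or guardian and the usual provider, and give the site liaison for hospital-recruited dyads or a resource list for social-media dyads. Send all parents the same general resource list with the post-survey, so that no individual score is disclosed. Record this in 2.21.
3. **Leave direct notification to the IRB.** Notification of a score from PI to parent is optional. It would need prior disclosure in the parent consent, the assent, the HIPAA authorization, 2.20 and 2.23.

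The cost is one amendment, one automatic REDCap message and one resource list, with no new visit, item, endpoint or committee. The downside is that some messages will reflect ordinary fluctuation.
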